1.3 Purpose and Objectives of the Study

The primary objective of the proposed study is to directly address this critical need by preliminarily testing the efficacy of ketamine in reducing opioid use and depression symptoms among individuals (N=30) with concurrent OUD and MDD who have failed to maintain abstinence despite treatment with a standard of care pharmacotherapy for OUD (i.e. buprenorphine, methadone or naltrexone). Effects on related symptoms and psychiatric conditions (e.g., cravings, motivation to quit, and anxiety symptoms) will also be explored. To accomplish this, we will use an intent-to-treat, double-blind, randomized clinical trial to compare the efficacy of ketamine to placebo control over a twice-weekly treatment schedule for four weeks. We will examine standardized, repeated dependent measures of clinical outcomes at baseline and multiple time points after the first treatment (48h to 8 weeks post initial treatment) with primary outcomes assessed at one month following the first treatment.

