Results from several meta-analyses indicate that ketamine can induce ultra-rapid improvements in depression and suicidality (Han et. al., 2016; Wilkinson et. al., 2017). This remission is most enduring in individuals with a family history of substance use disorders (Niciu et al., 2014). It is widely accepted that all currently approved pharmacotherapy classes for depression (serotonin reuptake inhibitors, monoamine oxidase inhibitors, and tricyclic antidepressants) are associated with a delayed onset of anti-depressant activity of 2-4 weeks. A meta-analysis of nine high-quality studies showed that ketamine was significantly more effective than placebo in reducing symptoms of major depressive disorder at 24 hours, 72 hours, and 7 days post-infusion (Han et. al., 2016). Additionally, results from a recent meta-analysis of ten clinical trials showed accumulating evidence that ketamine can significantly reduce suicidal ideation within 24 hours with moderate to large effect sizes (Wilkinson et. al., 2017). The overall duration of anti-depressant response was found to last between 3-12 days (Andrade, 2017). However, in a subgroup analysis, positive family history of alcoholism was found to be associated with a significantly longer duration of anti-depressant efficacy, averaging 17 days for the family history positive group and 3.6 days for the family history negative group (Niciu et. al., 2014). This suggests that the genetics underlying substance use confer a stronger response to the effects of ketamine.

Clinical Trials for Substance Use Disorder Treatment

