12.2 Hypotheses for Analyses

Feasibility Hypothesis: From the cohort of individuals completing the initial prescreening assessment, a 75% study enrollment rate will be deemed feasible. Therefore, we anticipate that 40 individuals will be needed to complete prescreening so that 30 participants will enroll in the study. Of the individuals enrolling in the study, we anticipate 60% of participants will *complete* the study protocol. *Completion* is defined for the study purposes as completing at least 75% of the study visits.

Hypothesis 1: Ketamine will result in significantly greater reduction in depression symptoms as compared to placebo at one-month. To test this hypothesis, we will employ repeated measures ANOVA using linear mixed models approach to assess reduction on the total score of the MADRS.

Hypothesis 2: Ketamine will result in significantly greater reduction in frequency of opioid use as compared to placebo at one-month. To test this hypothesis, we will treat the percent days using opioids (TLFB) as a continuous variable and analyze using linear mixed models approach. Abstinence at one-week (on UDS) will be compared by intervention groups using logistical regression analyses. An arcsine square root or logit transformation may be considered to stabilize variance of the proportions.

Hypothesis 3: Response to ketamine will be influenced by changes in motivation to quit (URICA) and qualities of psychoactive perceptual experience (HMS). To test this hypothesis, we will employ repeated measures ANOVA using linear mixed models approach.

Alternate Approaches: Diagnostics of the residuals will be performed to test the assumptions of the analysis. If the assumptions are found to be inadequate, alternative methods of analysis (e.g. ordinal logistic regression or Poisson regression) will be considered.

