The primary dependent variables in all three analyses will be intervention group (ketamine or placebo), time (number of days), and the interaction between the two. Main hypothesis of interest will be the interaction and the post-hoc comparison at the one month after the first intervention. We anticipate the study population to include participants that are currently on antidepressants as well as those that are not. We considered stratifying randomization by this variable, however since the proporption of participants on antidepressants at baseline is expected to be small, this will be considered as an independent variable in the statistical analysis. To account for within subject correlations, several structures, such as spatial autocorrelation (to accommodate unequal time points), and AR(1) symmetry, will be examined. Diagnostics will be considered. An arcsine square root transformation may be considered to stabilize variance of the proportions. In all of the analyses, covariates will be considered to examine mediations. In a secondary analysis based on the spaghetti plots, we will consider linear and non-linear models of outcomes as a function of time. Specifically, over the 8-week follow-up period, we will examine if there exists a threshold point in time where the effect of ketamine plateaus. To achieve this, treating the joint-point as unknown, we will fit segmented regression models using non-linear mixed models.

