12.3 Justification of Sample Size

PROTOCOL TITLE: Ketamine for the Treatment of Opioid Use and Depression Version Date: December 20, 2021

For a 75% anticipated enrollment rate from the initial prescreened sample of 40 individuals, feasibility can be estimated within a margin of error of 14% with 95% confidence. Similarly, assuming a 60% rate of study enrollment of eligible participants, with a sample size of 30 we can estimate feasibility within a 17% margin of error with a 95% confidence interval. This study is powered to estimate the effects of ketamine on significant reduction in MADRS symptoms at the end of one month (see Hypothesis 1). Over the course of a two-year study, we estimate that we will be able to recruit 15 patients in each of the two intervention arms (2/month over 15 months). At 80% power, this sample size will allow us to detect a minimum difference in MADRS scores of 14.4 at one month between the ketamine and the placebo groups in a study design with 7 repeated measurements having a AR(1) correlation of 0.9, and a standard deviation of 15.8, with a significance level of 0.050 (Singh et al., 2016; Niciu et al., 2014). While we will examine changes in depression severity as a continuous variable, we will also examine other clinically accepted changes in depression severity such as response (defined as a 50% reduction in symptom severity from baseline) and remission (defined as below the threshold for mild depression which is a score of 6 on the MADRS). Baseline averages for the MADRS scores for this population will be assumed to be 34 (Niciu et al., 2014; Han et al., 2016; Singh et al., 2016). The minimum difference in MADRS of 14.4 is anticipated to be approximately 50% of the baseline measurements. Although there is limited information on the effectiveness of ketamine in the treatment of addiction, a sample of 30 subjects (15 in each arm) will provide adequate power to detect an 22% difference between the two groups in the percent of days abstinent from opioid use using the same longitudinal design as described above with 7 time points (Hypothesis 2). For this calculation, we assumed an AR(1) correlation of 0.9 and a standard deviation of 25% at a significance level of 0.05; an arcsine transformation was used for variance stabilization. Over the 8-week follow-up period, we will examine if there exists a threshold point in time where the effect of ketamine plateaus. To achieve this, we will use a segmented regression analysis using non-linear mixed models. We will take all efforts to keep dropouts to a minimum. However, our past experience suggests the rates of dropout are up to 20%. This could reduce the sample size per group to 12 and 12. The corresponding differences we could detect would be a minimum MADRS score difference of 16.1 and a 26% difference between groups in terms of the percent of days abstinent from opioid use. No interim analyses are planned.

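### Section 12.2 leaves the coding of time and the analysis window open; read as a straight line in days over all MADRS visits, its interaction and one-month comparison capture the planned 14.4-point effect poorly

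*Combined protocol and SAP*

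**What the plan says.** Section 12.2 gives the model terms for all three hypotheses, and the start of the sentence on its main test, as "intervention group (ketamine or placebo), time (number of days), and the interaction between the two. Main hypothesis of interest will be the interaction". In full, that sentence names two targets: "Main hypothesis of interest will be the interaction and the post-hoc comparison at the one month after the first intervention". For Hypothesis 1 the method is: "we will employ repeated measures ANOVA using linear mixed models approach to assess reduction on the total score of the MADRS". The shape of the time course appears only under a secondary analysis guided by spaghetti plots, where "we will consider linear and non-linear models of outcomes as a function of time".

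Section 1.3 describes measurement at "multiple time points after the first treatment (48h to 8 weeks post initial treatment) with primary outcomes assessed at one month". In Table 2 (section 10.3) MADRS is taken at baseline, Tx2, Tx4, Tx6, Tx8 and three follow-up visits after the last dose. That is eight occasions, of which five fall by Wk 4. Section 12.3 sizes the trial for 14.4 MADRS points at one month "in a study design with 7 repeated measurements having a AR(1) correlation of 0.9".

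Sections 10.1 and 12.1 let placebo participants take ketamine from Wk 5. No section mentions visit as a categorical factor or limits the confirmatory model to Wk 4.

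**The concern.** Time given as a number of days reads most naturally as a numeric covariate. The interaction is then a difference between two straight-line slopes, and a one-month comparison from that model is a point on the fitted lines, not the difference observed at that visit.

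Hypothesis 1 is about a difference at one month. The background (section 2.0) cites a ketamine benefit present at 24 hours, and says of its length: "The overall duration of anti-depressant response was found to last between 3-12 days". An effect that arrives early and then holds or fades is not a steady divergence, and a straight line fits it badly. The trial could show the full planned difference at Wk 4 and still miss on the interaction, with a one-month estimate that is too small. Two analysts following section 12.2 could also fit different models and reach different conclusions from the same data.

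**Working it through.** **Inputs from the plan (section 12.3).** 15 per arm (12 after 20% dropout), SD 15.8, effect 14.4 at one month, AR(1) correlation 0.9, significance level 0.05 (two-sided assumed).

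**The plan's own figure.** The mean AR(1) correlation over 7 measurements is [7 + 2(6×0.9 + 5×0.81 + 4×0.729 + 3×0.6561 + 2×0.59049 + 0.531441)]/49 = 39.093/49 = 0.798. Then (1.960 + 0.842) × 15.8 × √(2 × 0.798/15) = 14.4, and with 12 per arm 16.1. Both stated values reproduce. They match a group difference averaged over seven visits. A single visit would give 16.2 and 18.1. The stated 80% power is therefore not power for a slope.

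**Assumptions for the check.** MADRS days are 0, 3, 10, 17, 24, 31, 38 and 52. The benefit is 0 at baseline and 14.4 at Tx2 to Tx8. After that it is either 10, 6 and 2 (fade) or 14.4 throughout (held). No placebo participant crosses over. The documents do not say whether 0.9 applies per week or per visit, so both are shown, with a constant correlation of 0.6 as a third case.

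**Method.** The vector of between-arm mean differences has variance V = (2 × 15.8²/15)R = 33.3R, where R is the correlation matrix. With X = [1, day] and δ the true differences, b = (X′V⁻¹X)⁻¹X′V⁻¹δ. Two-sided power is Φ(b₁/SE − 1.96) + Φ(−b₁/SE − 1.96). The fitted Wk 4 difference is b₀ + 24b₁. A positive slope favours ketamine.

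| Data used and true profile | Correlation | Slope per day (SE) | Power | Fitted Wk 4 difference (true 14.4) |
|---|---|---|---|---|
| All visits, fade | 0.9 per week | 0.03 (0.116) | 6% | 3.5 |
| All visits, fade | 0.9 per visit | -0.12 (0.107) | 19% | 3.7 |
| All visits, fade | constant 0.6 | -0.10 (0.077) | 27% | 9.2 |
| All visits, held | 0.9 per week | 0.27 (0.116) | 64% | 8.6 |
| All visits, held | 0.9 per visit | 0.14 (0.107) | 24% | 8.8 |
| All visits, held | constant 0.6 | 0.14 (0.077) | 44% | 12.9 |
| Wk 0-4 only | 0.9 per week | 0.60 (0.187) | 89% | 15.3 |
| Wk 0-4 only | 0.9 per visit | 0.33 (0.193) | 40% | 12.2 |
| Wk 0-4 only | constant 0.6 | 0.40 (0.185) | 58% | 16.8 |

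First row in full: 0.0289/0.1156 = 0.25, so power is 6%; the fitted value is 2.79 + 24 × 0.0289 = 3.5. Where the slope is negative, nearly all of the 19% and 27% are rejections in the wrong direction.

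**Other visit days.** With days 0, 10, 17, 24, 31, 38, 45 and 59, AR(1) 0.9 per visit or per week, and three other fades, slope power is 5-11% and the fitted Wk 4 difference 2.5-4.5. With the effect held to Wk 8, power is 61-75%. On baseline to Wk 4 only, it is 82-96%.

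**Visit as a factor.** For baseline against Wk 4, SE = √(33.3v), with v = 2(1 − r) for change and v = 1 − r² with baseline adjustment.

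| r | Change: SE, power | Baseline-adjusted: SE, power |
|---|---|---|
| 0.9^(24/7) = 0.697 | 4.49, 89% | 4.14, 94% |
| 0.9⁴ = 0.656 | 4.79, 85% | 4.35, 91% |
| 0.6 | 5.16, 80% | 4.61, 88% |

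With 12 per arm these become 70-82% and 80-88%. They do not depend on what happens after Wk 4. All powers are normal approximations and slightly optimistic at N = 30.

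**The case against.** A reader might infer that the plan commits itself to a slope test bound to fail. The documents do not support that, for five reasons.

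- The interaction is not the only target. The same sentence names a one-month comparison, and Hypothesis 1 is worded at one month. This stands, but it rescues the plan only if that comparison is not read off a straight line.
- Linear time is inferred. Days may be given only as the unit, and they are needed for the spatial correlation structure. Repeated measures ANOVA with post-hoc comparisons fits visit as a factor equally well. Linear as well as non-linear time models are placed in a secondary analysis, which could mean that the main model is neither. This stands as ambiguity. Residual diagnostics and spaghetti plots do not settle it, because they leave the choice until the data are seen.
- The window is not fixed. Section 12.1 places the main outcomes at Wk 4, and on Wk 0-4 data the slope is well away from zero. Seven measurements cannot be reached for MADRS without follow-up visits, but section 12.3 uses the same seven for opioid use, which Table 2 records at all twelve visits. The count is weak evidence of the window.
- The fade is an assumption. The 3-12 days come from background literature, not from a forecast after eight doses. The same section cites a 17-day average with a family history of alcoholism, and section 12.2 looks for a plateau. The held rows answer this: without any fade the fitted Wk 4 difference is still 8.6-12.9.
- MADRS is secondary in section 4.2 and the efficacy aims are preliminary. Table 2 labels MADRS a primary outcome, but section 4.1 gives that place to feasibility.

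**Conclusion.** The concern holds conditionally. Section 12.2 does not fix the coding of time, the visits in the model or a single confirmatory contrast. On its plain reading the two named targets capture an early effect poorly. Slope rejection is about 6-27% with the assumed fade, and the slope can take the wrong sign. Power is about 24-64% if the effect is held to Wk 8. The fitted Wk 4 difference is about 3.5-9.2 and 8.6-12.9 respectively, against a true 14.4. If only Wk 0-4 data were used, power would be about 40-89% on the same visit days, so a near-zero slope is not a general result.

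These figures rest on assumed visit days, post-treatment profiles and correlations. Optional ketamine in the placebo arm from Wk 5 was not modelled; it can further distort any slope that uses follow-up visits. The point concerns the main efficacy test, not the feasibility outcomes.

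**What to change.** In section 12.2, code time as scheduled visit (categorical) and keep days only for the spatial correlation structure. State which visits enter the model. Make the baseline-adjusted group difference in MADRS at the Wk 4 visit (Tx8) the single pre-specified test of Hypothesis 1. Report the overall group-by-visit interaction and any slope in days as supportive. Settle this before outcomes are examined by arm.

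The same time coding is reasonable for Hypothesis 2, but no calculation was made for percent days using opioids.

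The cost is a wording change and a few degrees of freedom for the visit terms. No extra visits, data or participants are needed.

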10.6 Intervention Visit Procedures

Prior to administration of the study compounds, participants will complete self-report questionnaires, urine testing, and clinical assessments. They will subsequently complete a 10-minute mindfulness-based psychological relaxation exercise and fill out a questionnaire regarding their study goals. Participant will be asked to disinfect their shoulder using an alcohol wipe, and the study physician will then administer the medication by intramuscular administration into the participant's deltoid muscle. Vital signs will be monitored prior to treatment, and at 45 and 90 minutes post-treatment, and blood oxygen levels will be continuously monitored using pulse oximetry. If during the post-administration observation period, ketamine administration causes an increase in systolic or diastolic blood pressure >30 mm Hg from baseline, or an increase in pulse rate >30 bpm from baseline, the measurements should be repeated after the patient has been in a resting position for 10 minutes. If the criterion is still met, then that patient will not receive further administration of ketamine and will be withdrawn from the study. After completion of the injection, participants will be monitored for 120 minutes, during which time they will undergo debriefing and complete assessments of their perceptual experience of the intervention. We will evaluate the effects of a twice weekly interventions for 4 weeks, and monitor outcomes over an additional 4-week follow-up period to inform pharmacotherapy frequency in future clinical trials. Follow-up visits may be conducted by telehealth.

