12.0 DATA MANAGEMENT

12.1 Data Analysis Plan

Baseline demographic characteristics will be collected and descriptive statistics will be used to characterize participants. Data will be collected and managed using the secure REDCap (Research Electronic Data Capture) database. Descriptive statistics for primary outcomes will include 1) the percentage of individuals completing informed consent out of the number of individuals eligible on the

initial screening and 2) the percentage of individuals that complete informed consent which complete the full protocol. Other descriptive statistics for the sample population will be analyzed, and baseline characteristics that are found to be significantly associated with other outcome measures will be included as covariates. Spaghetti plots will be produced to guide modeling outcomes as a function of time. All analyses will be conducted based on intention to treat. Subjects assigned to Group B (placebo) who complete Study Wk4 (at which time main outcomes are assessed), may choose to receive 8 ketamine treatments before completing follow-up visits. To preserve study blinding, subjects who are among the final 6 subjects being enrolled will not be unblinded until primary outcomes are assessed for all 30 subjects.

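### The plateau analysis fits one unknown joint-point across the end of dosing, so loss of effect after the last injection can hide an on-treatment plateau or pull the joint to the point where injections stop

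*Combined protocol and SAP*

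**What the plan says.** Section 12.2 describes a secondary analysis, guided by spaghetti plots, in which "we will consider linear and non-linear models of outcomes as a function of time". Its specific aim is that "over the 8-week follow-up period, we will examine if there exists a threshold point in time where the effect of ketamine plateaus", and the method is that "treating the joint-point as unknown, we will fit segmented regression models using non-linear mixed models". Section 12.3 repeats the aim and method but gives no power or precision figure for it.

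The window is defined in section 1.3: outcomes are measured "48h to 8 weeks post initial treatment", on a "twice-weekly treatment schedule for four weeks". So about half of the 8 weeks is on treatment and half is not. Section 10.6 says the trial will "monitor outcomes over an additional 4-week follow-up period to inform pharmacotherapy frequency in future clinical trials". Table 2 schedules the MADRS at baseline, Tx2, Tx4, Tx6 and Tx8, then 1, 2 and 4 weeks after dosing.

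On how long an effect lasts, section 2.0 reports: "The overall duration of anti-depressant response was found to last between 3-12 days". It adds averages of 17 and 3.6 days for people with and without a family history of alcoholism.

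Under section 12.1, Group B participants who finish Wk 4 "may choose to receive 8 ketamine treatments before completing follow-up visits". For those who opt in, Wk 5-8 is a period on ketamine.

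**The concern.** A plausible Group A course has three phases: improvement, possibly a plateau, then loss once injections stop. One joint gives two segments. If the third phase occurs, the second segment has to average the plateau and the loss, or the joint has to move to the boundary between dosing and follow-up.

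The plan has no term for the end of dosing, no definition of a plateau (such as zero slope after the joint) and no rule for concluding that there is no joint. A free-joint model returns a joint for any data.

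At stake is the trial's description of its own time course. Section 10.6 wants treatment and follow-up to inform later trials, and this is the only analysis in section 12 aimed at when the effect stops growing.

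**Working it through.** **The plan's own figure.** Section 12.3 gives no figure for the joint-point, so its MADRS calculation serves to confirm the noise model. With 7 measurements and AR(1) 0.9, the mean of the correlation matrix is 0.798. Then (1.960 + 0.842) × 15.8 × √(2/15) × √0.798 = 14.44 (stated 14.4). With 12 per arm it is 16.14 (stated 16.1). SD 15.8 and AR(1) 0.9 are therefore used below.

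**Noise-free fits.** Inputs from section 12.3 are a baseline of 34 and a maximum fall of 14.4. Assumed visit days, with injections 3-4 days apart, are 0, 3, 10, 17, 24 (Tx8), 31, 38 and 52. The trajectory shapes are assumptions: a linear fall to day p, level to day 24, then linear loss over L days. The model is y = a + b·t + c·max(t − k, 0), fitted by least squares with k searched in 0.5-day steps. The second slope is b + c.

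Full loss, with L = 3.6, 7, 12, 17 and 28 days:

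| True course | Fitted joint (day) | Second slope (points/day) |
|---|---|---|
| Still falling to day 24, no plateau | 18.5, 18.5, 21.0, 22.5, 24.0 | +0.42, +0.42, +0.49, +0.51, +0.51 |
| Plateau from day 10 | 11.0 to 12.5 | +0.44 to +0.49 (true on-treatment value 0) |
| Plateau from day 14 | 14.0, 14.0, 15.0, 15.5, 19.0 | rising |

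One case can be checked by hand. With no plateau and L = 28, the course is exactly two segments: slope −14.4/24 = −0.60, a joint at day 24, then +14.4/28 = +0.51.

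- Partial loss: with 25% lost by day 52, plateaus from days 10 and 14 give joints at 11.0 and 14.5 and a second slope of +0.11. With 25-50% lost, the slope is about +0.1 to +0.2.
- No loss: the 8-week fit recovers day 10 or 14 exactly, with slope 0.
- Visits to Tx8 only: the fit recovers day 10 or 14 with slope 0. When there is no plateau it gives equal slopes (−0.6, −0.6).

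**With noise.** The between-arm difference was simulated on the study-week scale: peak 14.4, 15 per arm, 4000 runs per shape, Group B treated as staying on placebo. Flat means that the interval for the post-joint slope includes zero.

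| True difference between arms | Median joint | Joint in Wk 3.5-5 | Flat after joint |
|---|---|---|---|
| Grows to Wk 4, all lost by Wk 6 | Wk 4.0 | 85% | 27% |
| Grows to Wk 4, all lost by Wk 8 | Wk 4.0 | 89% | 4% |
| Grows to Wk 4, half lost by Wk 8 | Wk 4.0 | 76% | 52% |
| Plateau Wk 2-4, all lost by Wk 6 | Wk 2.25 | 12% | 25% |
| Plateau Wk 2-4, all lost by Wk 8 | Wk 2.25 | 21% | 5% |
| Plateau from Wk 2, held to Wk 8 | Wk 2.0 | 4% | 93% |

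On the day scale, a true day-10 plateau lost after dosing looks flat in about 6-26% of 8-week fits and in about 92% of fits restricted to visits up to Tx8.

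**No change point.** With no effect, or a straight line to Wk 8, a joint is returned in every run (median Wk 3.0-3.25). It is nominally significant in about 18% of runs at the 1-df cutoff of 3.84, which ignores the search over k. Restricting the window does not cure this: with no on-treatment plateau, the joint from visits up to Tx8 has an interquartile range of about day 4-17.

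**Sensitivity.** At 12 per arm, the share of growing-then-lost runs with the joint in Wk 3.5-5 is 73-85%. With AR(1) 0.5 and 15 per arm it is 45-56%.

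**The case against.** The strongest reply is that a joint is not a plateau. A competent analyst who sees a joint near Wk 4 followed by a rising slope would report loss after dosing. That stands: in the growing-then-lost cases the post-joint slope shows loss in 48-96% of runs. A reader might infer that the planned model reports a plateau whenever none exists, or that post-dosing loss always drives the joint. The documents support neither. A reader might also infer that the model cannot locate an early plateau, but the joint usually stays close to it (day 11.0-12.5 for a true day 10). What goes wrong there is the slope after the joint.

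It can also be said that loss after dosing is not certain. Section 2.0 gives 17 days with a family history of alcoholism and suggests a stronger response where substance use is heritable. This too stands in part. With benefit fully retained, the planned model is sound. With partial loss the spurious slope is shallow, and noise would hide it more often.

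Finally, section 12.2 asks whether a threshold exists, allows straight-line models and uses plots as a guide. That shows intent, but it gives no rule for choosing between models and no criterion for a plateau. Section 10.6 mentions treatment frequency without naming this analysis, so its influence on later trials is an inference.

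**Conclusion.** The concern holds in a conditional form. The stated method spans the end of dosing with one free joint and no end-of-dosing term, while the protocol's own background suggests that the effect fades within days. If the effect is fully lost, a real on-treatment plateau is usually masked (flat in about 6-26% of fits). If the effect is still growing at Tx8, the joint marks the stop of injections, and the slope after it can still pass as flat in 4-52% of runs, depending on how much is lost.

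These sizes rest on assumed trajectory shapes and visit days, a 14.4-point peak, SD 15.8 and AR(1) 0.9. The end-of-dosing joint is less frequent with weaker correlation. The problem exists in Group A alone; optional ketamine in Group B further erodes the placebo series after Wk 4. The analysis is secondary, and the primary feasibility outcomes and the one-month comparison do not depend on it. The plan should be changed before analysis, but the trial's main results are not at risk.

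**What to change.** In sections 12.2 and 12.3:

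1. Search for the free joint-point only within the dosing period, baseline to Tx8.
2. Add a fixed knot at each participant's last injection. Model Wk 5, 6 and 8 as a separate segment and report it as durability.
3. Declare a plateau only if the on-treatment slope after the joint is compatible with zero and the joint improves on a straight line by a test valid for an unknown change point, such as a parametric bootstrap. Report the interval for that slope, because with few visits a slope can be compatible with zero merely through imprecision.
4. Exclude Group B data from the placebo series once optional ketamine begins.

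The cost is SAP wording, with no new data. The on-treatment search rests on 5 MADRS times, so the joint will be imprecise. The BDI-II, scheduled at every visit (9 times from baseline to Tx8), can be a supportive series only, since sections 4 and 12 give it no role. Excluding Group B after crossover leaves few placebo observations in Wk 5-8 if many opt in, so durability would then be described mainly within Group A.
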